3.1.1.2 Secondary Estimand

The secondary estimand will be referred to as the 'treatment policy estimand'. The treatment policy estimand assesses the treatment effect regardless of adherence to treatment and provides a broad perspective of the treatment effect in clinical practice in the selected population of patients. This estimand is in line with the 'intention to treat' principle and provides a robust assessment of the efficacy of the SQ tree SLIT-tablet.

The treatment policy estimand can similarly be described by:

- A. **Treatment:** SQ tree SLIT-tablet or placebo, with rescue medication taken as required
- B. **Population:** children and adolescents (5-17 years of age) with moderate to severe AR/C caused by pollen from birch
- C. **Variable:** Average TCS during the BPS
- D. **How to account for intercurrent events:** regardless of whether subjects complete treatment for the planned duration (treatment policy strategy)
- E. **Population summary:** Absolute difference between treatments

A treatment policy strategy will be used to address the intercurrent event of discontinuation of trial treatment. As such, if a subject discontinues trial treatment, all available diary data will be included in the analysis, regardless of adherence to treatment. Details of the handling of IEs and missing data are provided in section 6.3.3.2.

3.1.1.3 Intercurrent events

The IE that has been identified as relevant is discontinuation of trial treatment. No additional IEs were identified to have an impact on the overall efficacy assessment.

Due to the long duration of allergy immunotherapy clinical trials, rescue medication is dispensed to every subject for ethical reasons. The use of rescue medication is, therefore, part of the treatment policy and as such, it is not classified as an IE for this trial.

The number of IEs will be summarised by reason for discontinuation of trial treatment and treatment.

3.1.1.4 Estimands for key secondary objectives

The trial product estimand and treatment policy estimand, specified for the primary objective in sections 3.1.1.1 and 3.1.1.2 respectively, are defined similarly for each of the key secondary objectives, where the relevant key secondary endpoint of interest is specified in attribute C.

[figure not shown]
3.2 Trial design

This is a phase III, randomised, parallel-group, double-blind, placebo-controlled, multi-regional trial in children (5-11 years) and adolescents (12-17 years) with AR/C, with or without asthma, induced by pollen from birch. Based on previous trials, it is anticipated that most subjects allergic to birch will also have AR/C induced by pollen from the birch homologous group.

Approximately 1000 subjects were to be randomised (1:1) and receive treatment with the SQ tree SLIT-tablet or placebo. The randomisation was stratified by geographical location (country) and by age group (5-11 years and 12-17 years).

[figure not shown]
The trial consisted of 3 periods: a screening period, a treatment period, which included pre-seasonal and co-seasonal treatment, and a follow-up period (Figure 1). The trial consisted of 2 cohorts; subjects in cohort 1 were randomised in 2021 and received treatment during the pollen seasons of 2022; subjects in cohort 2 were randomised in 2022 and received treatment during the pollen seasons of 2023.

Figure 1: Overall trial design

The screening visit took place up to approximately 6 months prior to randomisation. Once randomised, subjects were treated for at least 12 weeks prior to the start of the TPS. Treatment continued until 1 week after the end of the TPS, corresponding to up to approximately 12 months of treatment.

[REDACTED]
[REDACTED]
[REDACTED] Open-label rescue medication for allergic rhinoconjunctivitis was provided during the TPS [REDACTED]. Open-label asthma medication was provided to subjects with asthma during the TPS [REDACTED]. A follow-up phone visit was planned 1 week after the final treatment.

3.2.1 Flow chart

The flow chart of the trial assessments by visits are shown below in Table 2.

Table 2: Flow chart

Visit ID:	V1	TC1 ²	V2	V3	V4	TC2	TC3	V5	TC [REDACTED]	V6	TC4	UV ³
Name of visit	Screening	Retention	Randomisation	Off season	Pre-TPS	Start of TPS	Pre-BPS	In season BPS	Only for cohort 1 subjects also [REDACTED] [REDACTED] [REDACTED]	End-of-treatment	Follow-up	Unscheduled
Scheduled week	1-26 weeks prior to V2	4-12 weeks prior to V2	At least 12 weeks prior to expected start of TPS ⁴	4 weeks after V2	2 weeks prior to expected start of TPS		2 weeks prior to expected start of BPS	2 weeks after expected start of BPS ⁵	1 week after expected end of TPS	1 week after expected end of TPS	1 week after V6	
Visit window				+7 days	-14 to +7 days	-4 days	+7 days	+7 days	+7 days	+7 days	+7 days	
Administrative procedures												
Informed consent ⁷	X											

² Only required if V1 (screening) is performed more than 12 weeks prior to randomisation.

³ Unscheduled visits should be conducted as necessary. The evaluations/examinations listed with brackets should only be performed if deemed necessary by the investigator.

⁴ Randomisation (V2) must be performed at least 12 weeks prior to expected TPS but no later than 31 October.

⁵ Visit 5 can be scheduled based on the actual BPS start date.

⁶ In cohort 1 subjects also [REDACTED] V6 is to be performed 1 week after the expected end of [REDACTED]. End of [REDACTED] can be no later than 31 August 2022.

⁷ Obtain written informed consent for the trial, storage of serum samples in the ALK Research Biobank, and for pharmacogenetics testing before any other trial procedures are performed.

Visit ID:	V1	TC1 ²	V2	V3	V4	TC2	TC3	V5	TC █	V6	TC4	UV ³
Name of visit	Screening	Retention	Randomisation	Off season	Pre-TPS	Start of TPS	Pre-BPS	In season BPS	Only for cohort 1 subjects also █ █	End-of-treatment	Follow-up	Unscheduled
Inclusion/exclusion criteria	X		X									
Randomisation			X									
Demography	X											
Smoking habit	X											
Medical history	X											
Record prior and concomitant medication	X	X	X	X	X	X	X	X	X	X	X	X
TC to ensure that subject is still interested in the trial		X										
Dispense IMP			X		X			X				(X)
Instruct the subject in use of IMP			X									(X)
Collect IMP and perform drug accountability					X			X		X		
Perform IMP compliance check				X	X			X		X		
Dispense rhinoconjunctivitis and asthma rescue medication					X			X				(X)
Collect rescue medication and perform drug accountability								X		X		
Handout eDiary					X							

Visit ID:	V1	TC1 ²	V2	V3	V4	TC2	TC3	V5	TC █	V6	TC4	UV ³
Name of visit	Screening	Retention	Randomisation	Off season	Pre-TPS	Start of TPS	Pre-BPS	In season BPS	Only for cohort 1 subjects also █ █	End-of-treatment	Follow-up	Unscheduled
Instruct in the use of the eDiary incl. training in symptom scoring					X	X	X	X	X			
Show and/or discuss trial video					X	X	X	X				
Inform that TPS is starting						X						
Clinical procedures/assessments												
Physical examination	X		X							X		(X)
Height			X							X		(X)
Weight	X		X							X		(X)
Vital signs	X									X		(X)
Lung function test ⁸			X							X		(X)
SPT ⁹	X		(X)									
Assess AEs	X	X	X	X	X	X	X	X	X	X	X	X
Assess symptoms of eosinophilic oesophagitis	X		X	X	X	X	X	X	X	X	X	X
Intake of IMP at clinic			X									

⁸ Measure FVC and FEV₁ while subject is on their usual asthma medication (if applicable) following at least a 6 hour washout of SABA.

⁹ To be taken after a urine pregnancy test (if applicable). A positive SPT is defined in the SPT guideline. Briefly, a positive SPT is defined as a wheal size of ≥ 3 mm. If medication that could interfere with the SPT, according to prohibited and restricted medication table, has not been washed out, the SPT must be performed at V2 after the interfering medication has been washed out.

Visit ID:	V1	TC1 ²	V2	V3	V4	TC2	TC3	V5	TC [REDACTED]	V6	TC4	UV ³
Name of visit	Screening	Retention	Randomisation	Off season	Pre-TPS	Start of TPS	Pre-BPS	In season BPS	Only for cohort 1 subjects also [REDACTED] [REDACTED]	End-of-treatment	Follow-up	Unscheduled
All subjects (except for cohort 1 subjects with [REDACTED])												
Daily eDiary recording:												
•AR/C symptoms												
•AR/C medication												
•[REDACTED]												
[REDACTED]												
[REDACTED]												
[REDACTED]												
[REDACTED]												
[REDACTED]												
Weekly eDiary recording:												
•RQLQ(S) ¹⁰												
Cohort 1 subjects with [REDACTED]												

¹⁰ RQLQ(S) should be performed only for subjects who were 12-17 years at the randomisation visit.

Visit ID:	V1	TC1 ²	V2	V3	V4	TC2	TC3	V5	TC [REDACTED]	V6	TC4	UV ³
Name of visit	Screening	Retention	Randomisation	Off season	Pre-TPS	Start of TPS	Pre-BPS	In season BPS	Only for cohort 1 subjects also [REDACTED] [REDACTED]	End-of-treatment	Follow-up	Unscheduled
Daily eDiary recording: •AR/C symptoms AR/C medication												
Cohort 1 subjects with [REDACTED]												
Daily eDiary recording: •[REDACTED] •[REDACTED] •[REDACTED] •[REDACTED] •[REDACTED] •[REDACTED] •[REDACTED] •[REDACTED] •[REDACTED] •[REDACTED] •[REDACTED] •[REDACTED]									X ----- X			
Weekly eDiary recording: RQLQ(S) ¹⁰												
Review eDiary recordings and compliance						X-----X						
Collect eDiary										X		

Visit ID:	V1	TC1 ²	V2	V3	V4	TC2	TC3	V5	TC [REDACTED]	V6	TC4	UV ³
Name of visit	Screening	Retention	Randomisation	Off season	Pre-TPS	Start of TPS	Pre-BPS	In season BPS	Only for cohort 1 subjects also [REDACTED] [REDACTED]	End-of-treatment	Follow-up	Unscheduled
PRQLQ ¹¹								X				
All subjects (except for cohort 1 subjects with [REDACTED]): •Global evaluation of treatment efficacy •TSQM-9										X		
Cohort 1 subjects with [REDACTED]: •Global evaluation of treatment efficacy TSQM-9									X			
Laboratory procedures/assessments												
Blood sample for specific IgE against Bet v	X											(X)
Blood and urine samples for safety laboratory assessments	X									X		(X)
Urine pregnancy test ¹²	X		X	X	X			X		X		(X)

¹¹ Perform PRQLQ interview, only for subjects who were 5-11 years at the randomisation visit.

¹² For female subjects of childbearing potential only, additional urine pregnancy tests should be performed during the trial, if a menstrual period is missed.

Visit ID:	V1	TC1 ²	V2	V3	V4	TC2	TC3	V5	TC [REDACTED]	V6	TC4	UV ³
Name of visit	Screening	Retention	Randomisation	Off season	Pre-TPS	Start of TPS	Pre-BPS	In season BPS	Only for cohort 1 subjects also [REDACTED] [REDACTED]	End-of-treatment	Follow-up	Unscheduled
Blood sample for Immunological assessments	X				X					X		(X)
Blood sample for biobank ¹³	X				X					X		(X)
Blood sample for pharmacogenetics ¹⁴										X		(X)

¹³ Only for subjects where informed consent for biobank sampling has been obtained.

¹⁴ Only for subjects where informed consent for pharmacogenetics sampling has been obtained.

3.2.2 Actual trial timelines

For cohort 2 the randomisation window was extended based on regional pollen data instead of dates for national pollen data used for cohort 1.

The schedule of cohorts is presented in Table 3.

Table 3:Schedule of cohorts

	Cohort 1	Cohort 2
First subject first visit	08-Apr-2021	10-Mar-2022
Last subject randomised	01-Nov-2021	21-Dec-2022
Last subject last visit	24-Oct-2022	31-July-2023

3.2.3 Randomisation

The randomisation list has been generated by the IRT provider and will not be accessible to trial personnel involved in the conduct of the trial, until the database has been locked. The randomisation was administered centrally via IRT and was stratified based on country and age group.

The randomisation codes will only be made available for data analysis when the clinical database has been locked and all PDs have been identified, evaluated, categorised, and closed.

4 Statistical hypotheses

4.1.1 Multiplicity adjustment

For the trial product estimand based on the primary efficacy endpoint and the key secondary efficacy endpoints, the analyses for the main estimators will be controlled for multiplicity to ensure a maximum overall type I error rate of 5% in the hypothesis testing of these endpoints.

The control for multiplicity will be performed through hierarchical testing, using a pre-specified order of hypothesis to be tested. For each endpoint, the null hypothesis to be tested is the hypothesis of no difference between placebo and active SQ tree SLIT-tablet. Let μ_1 denote the mean in the SQ tree SLIT-tablet group, and μ_2 denote the mean in the placebo group. Then the null hypothesis (H_0) and the alternative hypothesis (H_A) are given as follows:

$$H_0: \mu_1 = \mu_2 \text{ and } H_A: \mu_1 \neq \mu_2$$

The order of the hypotheses to be tested is:

1. The primary efficacy analysis of average TCS during BPS
2. The key secondary efficacy analysis of average TCS during TPS
3. The key secondary efficacy analysis of average DSS during BPS
4. The key secondary efficacy analysis of average DSS during TPS
5. The key secondary efficacy analysis of average DMS during BPS
6. The key secondary efficacy analysis of average DMS during TPS

The first hypothesis in the hierarchy will be tested at a two-sided 5% significance level. Testing will proceed to the second hypothesis only if the first test is statistically significant ($p < 0.05$). Similarly, testing will proceed to the next level of the hierarchy, only if the previous comparison is statistically significant at the 5% level. If a test is not statistically significant ($p > 0.05$) then no further testing within the hierarchy will be conducted. Thus, the 2nd, 3rd, 4th, 5th, and 6th hypothesis tests in the hierarchy will only be conducted if all previously tested hypotheses are statistically significant at the 5% level.

Furthermore, analysis of the quality of life endpoints will be included as the final steps in the testing hierarchy, where the order of the hypotheses to be tested is:

7. The secondary efficacy analysis of average weekly overall RQLQ score during the BPS
8. The secondary efficacy analysis of average weekly overall RQLQ score during the TPS
9. The secondary efficacy analysis of overall PRQLQ score during the BPS

Additional endpoints and analyses are supportive in nature and are not controlled for multiplicity.

5 Analysis sets

For the purposes of analysis, the analysis sets presented in

Table 4 are defined.

Table 4: Analysis set definitions

Participant analysis set	Description	Application
TAS	All subjects who signed informed consent and thus includes screening failures.	Outputs related to disposition.
FAS	All randomised subjects. Subjects will be analysed as randomised i.e., according to their randomised assignment of treatment.	Outputs related to baseline and efficacy outputs.
SAF	All randomised subjects who received at least one dose of IMP. Subjects will be analysed as treated i.e., according to treatment they actually received.	Outputs related to safety reporting.
SUB	Subjects in a random subset sample stratified by treatment group and age group for cohort 1.	Endpoints related to alder, hazel and oak specific IgE and IgG4, and birch, alder, and hazel specific IgE-BF.

[REDACTED]
[REDACTED]

The following DPS are defined:

DPS1: For subjects who complete the trial treatment, all data is included.

For subjects who discontinue trial treatment, all data collected after the time of trial treatment discontinuation will not be included for the trial product estimand.

DPS2: All data is included.

FAS and DPS1 are used to estimate the trial product estimand, FAS and DPS2 are used to estimate the treatment policy estimand and observed case.

6 Statistical analyses

Statistical analyses will be carried out by ALK, Biometrics, Hørsholm, Denmark. All computation will be performed using SAS, SAS® version 9.4 or later.

The analyses described in this section along with the supporting information supplied in section 9 and Appendix B specify the statistical analyses.

6.1 General considerations

Continuous data will be summarised by treatment group using mean, standard deviation, median, minimum, and maximum. Categorical data will be summarised by treatment using frequency tables displaying numbers and percentages. For the tabulations of data by visit an observed case approach is used.

All the statistical tests described in this document use a significance level of 5% and all tests and confidence intervals are two-sided. The null hypothesis is the hypothesis of no difference between treatment groups and the alternative to the null hypothesis is the hypothesis of difference. For each analysis the specific test is described in more detail.

The number of imputations will be increased from 1000 to 10000 if the actual significance level of the performed test is estimated to be between 4%-6%. This will be done to ensure the precision of estimated standard error, and thus the right hypothesis testing conclusion will be made.

Baseline values are defined as the latest available observation at or prior to the date of the first administration of IMP, unless otherwise defined.

Collected age at randomisation will be used to derive the medication score throughout the pollen season.

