⁵ Unscheduled visits should be conducted as necessary. The evaluations/examinations listed with brackets should only be performed if deemed necessary by the investigator.

⁶ Randomisation (V2) must be performed at least 12 weeks prior to expected TPS but no later than 31 October.

⁷ Visit 5 can be scheduled based on the actual BPS start date.

⁸ In cohort 1 subjects also V6 is to be performed 1 week after the expected end of a . End of a can be no later than 31 August 2022.

⁹ Obtain written informed consent for the trial, storage of serum samples in the ALK Research Biobank, and for pharmacogenetics testing before any other trial procedures are performed.

Clinical trial protocol	EudraCT No: 2020-004372-17	Date:	24-May-2020	Status:	Final	
Trial ID: TT-06	CONFIDENTIAL	Version:	3.0	Page:	19 of 99	

Visit ID:	V1	TC1 ⁴	V2	V3	V4	TC2	TC3	V5	тс	V6	TC4	UV ⁵
Name of visit	Screen- ing	Retention	Randomi- sation	Off season	Pre-TPS	Start of TPS	Pre-BPS	In season BPS	Only for cohort 1 subjects also	End-of-treatment	Follow- up	Unsched- uled
Instruct the subject in use of IMP			х									(X)
Collect IMP and perform drug accountability					Х			х		Х		
Perform IMP compliance check				х	Х			х		х		
Dispense rhinoconjunctivitis and asthma rescue medication					Х			х				(X)
Collect rescue medication and perform drug accountability								х		Х		
Handout eDiary					Х							
Instruct in the use of the eDiary incl. training in symptom scoring					х	х	х	x	х			
Show and/or discuss trial video					Х	Х	Х	Х				
Inform that TPS is starting						Х						
Clinical procedures/assessm	ents											
Physical examination	Х		Х							Х		(X)
Height			Х							Х		(X)
Weight	Х		Х							Х		(X)
Vital signs	Х									Х		(X)
Lung function test ¹⁰			Х							Х		(X)
SPT ¹¹	Х		(X)									
Assess AEs	X	Х	Х	Х	Х	Х	Х	Х	Х	Х	Х	Х
Assess symptoms of eosinophilic oesophagitis	х		х	Х	Х	Х	Х	х	х	Х	х	Х

¹⁰ Measure FVC and FEV₁ while subject is on their usual asthma medication (if applicable) following at least a 6 hour washout of SABA.
¹¹ To be taken after a urine pregnancy test (if applicable). A positive SPT is defined in the SPT guideline. Briefly, a positive SPT is defined as a wheal size of ≥3 mm. If medication that could interfere with the SPT, according to prohibited and restricted medication table, has not been washed out, the SPT must be performed at V2 after the interfering medication has been washed out.

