9.3 Treatment of severe allergic reactions/anaphylaxis

The subject/parent/caregiver will be provided with educational information regarding symptoms of anaphylaxis and treatment.

In the event of symptoms or treatment of anaphylaxis, the subject/parent/caregiver must immediately call the local emergency number and the 24-hour investigational site emergency number indicated on the subject identification card. An unscheduled visit will be arranged to further evaluate the subject. The investigator or designee must notify the Sponsor within 1 working day of first becoming aware of symptoms or treatment of anaphylaxis. The symptoms and/or circumstances that triggered symptoms or treatment of anaphylaxis must be clearly recorded on the eCRF.

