10 VISIT SCHEDULE

The assessments that should be performed at each visit are described in **Table 6**. The assessments are listed in the chronological order in which they should preferably be performed:

Visit ID	Assessments to be performed at the visit
Visit 1 (screening)	Visit window: 1 to 26 weeks prior to randomisation visit 2
	 Obtain written informed consent for the trial before any other assessment is performed Obtain written informed consent for collection and storage of serum samples in the ALK Research Biobank and for pharmacogenetic testing, if applicable, before any other assessments are performed Assess compliance with inclusion and exclusion criteria Obtain demographic data (sex, month and year of birth, race and ethnicity) Record smoking habits Record use of relevant prior and concomitant medications Perform physical examination Measure weight Measure vital signs Perform urine pregnancy test (if appropriate) No data is available for SPT in pregnant subjects, therefore for female subjects of child-bearing potential, perform the urine pregnancy test before SPT Perform SPT and evaluate results (to be performed at visit 2, if wash-out of concomitant medication is required) Assess AEs Assess symptoms of eosinophilic oesophagitis Collect blood and urine sampling for safety laboratory assessments Collect blood sampling for specific IgE against Bet v and immunological assessments If the specific consent has been obtained, collect the biobank blood sample
	 Schedule the date for the retention visit TC1 and/or visit 2 and complete this in the eCRF

Table 6Visit schedule

Clinical trial protocol	Date:	24-May-2020	
Trial ID: TT-06	Version:	3.0	
EudraCT No: 2020-004372-17	Status:	Final	
CONFIDENTIAL	Page:	50 of 99	

TC1 (Retention)	Visit window: 4 to 12 weeks prior to visit 2. Only required if screening is more than 12 weeks prior to randomisation				
	 Confirm subject's continued interest in trial participation Assess AEs occurring since the last visit Record concomitant medication Reconfirm date for visit 2 				
Visit 2 (Randomisation	Visit window: 1 to 26 weeks after screening visit 1				

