and first IMP administration)	 Re-assess compliance with inclusion and exclusion criteria Randomise the subject Record concomitant medication Perform physical examination Measure height and weight Lung function: All subjects who are 7 years of age or older must perform the lung function test related to Exclusion criterion 7. Subjects who are less than 7 years of age may not have to perform the lung function test depending on the following: 				
	If yes, the lung function test needs to be performed				
	 If no, can the subject produce reproducible FEV1 results if they are coached on how to do this? 				
	 If yes, the lung function test needs to be performed 				
	 If no, then the subject is exempt from performing the lung function test and the attempt to perform the lung function test is to be recorded in the subject journal 				
	 Perform urine pregnancy test, if applicable For subjects requiring wash-out of concomitant medication as per visit 1, SPT should be performed and results evaluated Assess AEs occurring since the last visit Assess symptoms of eosinophilic oesophagitis Dispense IMP to the subject Instruct the subject in how to use the IMP First intake of IMP at the clinic. The first dose will be administered at the clinic with a subsequent 30 minutes observation period Schedule the date for visit 3 				
	Visit window: 4 weeks after V2 (+ 7 days)				

Clinical trial protocol	Date:	24-May-2020	
Trial ID: TT-06	Version:	3.0	
EudraCT No: 2020-004372-17	Status:	Final	
CONFIDENTIAL	Page:	51 of 99	

Visit 3 (Off season)	 Record changes to concomitant medication Perform IMP compliance check (see Section 8.5) Assess AEs occurring since the last visit Assess symptoms of eosinophilic oesophagitis Perform urine pregnancy test, if applicable Schedule the date for visit 4
Visit 4 (Pre-TPS)	Visit window: 2 weeks prior to the expected start of TPS specified for the country/region (-14 to +7 days)

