6.9.2.2 Reporting of adverse events

AE is considered a TEAE if the time of onset is after the time of first dose of IMP and at most 7 days after last dose of IMP.

All TEAEs will be summarised by treatment group according to causality, severity (mild, moderate, severe), seriousness, action taken, outcome, and whether the event led to IMP discontinuation. The number of subjects in each treatment group, the number and frequency of

subjects having the event, as well as the number of events and proportion of events will be displayed. A similar summary table will be produced for all IMP-related TEAEs.

All TEAEs and all IMP-related TEAEs will be summarised (in separate tables) by treatment group, SOC, and PT, displaying number of subjects in treatment group, and number and frequency of subjects having the event. The tables will be sorted according to most frequent SOC and PT in the active treatment group, and the most common TEAEs (preferred term from MedDRA) defined as those that are present in at least 5% of subjects in the active treatment group will be marked.

Severe TEAEs will be listed only, if there are fewer than 10 events in total. Otherwise, severe TEAEs will also be summarised similar to how TEAEs are presented. The same applies for SAEs, IMP-related SAEs, TEAEs leading to IMP interruption, and TEAEs leading to IMP discontinuation.

For most frequent IMP-related TEAEs (present in at least 5% of subject in the active treatment group) onset and duration will be presented as follows: Average time to onset and average duration both in days, will be presented by PT and treatment. In addition, for day 1 of treatment average time to onset in day and minutes will be presented by SOC, PT, and treatment.

For the most frequent IMP-related TEAEs which are recurrent, the average daily duration and the average duration in days from first to last occurrence will be presented by SOC, PT and treatment.

Most frequent non-serious TEAEs in any arm (≥ 1 and $\geq 5\%$) will be summarised by system organ class and preferred term.

A table with the overall summary of the safety profile will be produced showing subjects with TEAEs, IMP-related TEAEs, IMP-related severe TEAEs, IMP-related treatment-emergent SAEs, IMP-related TEAEs leading to IMP discontinuation, and each type of IMP-related treatment-emergent ESI by treatment group.

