6.9.3 Additional safety assessments

Shift tables will be produced for physical examination, and laboratory assessments (chemistry, haematology, and urinalysis) for baseline to EOT.

In addition to above laboratory assessments (chemistry and haematology), vital signs and the pulmonary function test parameters (FVC, FVC percent predicted, FEV₁, and FEV₁ percent predicted) will be summarised by visit and treatment group.

Results from the pregnancy test for female subjects of child-bearing potential will be listed.

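### Baseline is cut off at the date, not the time, of first IMP intake, so a post-dose examination or laboratory value from dosing day can become the shift-table baseline

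*SAP*

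**What the plan says.** SAP 6.1 gives one general rule: "Baseline values are defined as the latest available observation at or prior to the date of the first administration of IMP". It allows exceptions ("unless otherwise defined"), but the SAP text contains no other baseline definition for safety measurements.

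Adverse events follow a clock-time rule. SAP 6.9.2.2 says: "AE is considered a TEAE if the time of onset is after the time of first dose of IMP".

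Baseline enters the safety outputs through SAP 6.9.3: "Shift tables will be produced for physical examination, and laboratory assessments (chemistry, haematology, and urinalysis) for baseline to EOT". SAP 6.11 adds that, for physical examination, the shift table replaces the by-visit summary planned in the protocol.

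On dosing day, Protocol section 10 (Table 6, visit 2) says: "The first dose will be administered at the clinic with a subsequent 30 minutes observation period". Physical examination and lung function stand above first intake in that list, but the sequence is only a preference: "The assessments are listed in the chronological order in which they should preferably be performed". The Protocol flow chart brackets physical examination, vital signs, lung function and safety laboratory samples under unscheduled visits, and its footnote 5 says: "The evaluations/examinations listed with brackets should only be performed if deemed necessary by the investigator". For symptoms or treatment of anaphylaxis, Protocol 9.3 says: "An unscheduled visit will be arranged to further evaluate the subject".

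**The concern.** A baseline value should describe the child before any exposure to IMP. Here the first exposure happens at the clinic, on a day when measurements may also be taken, and the rule cannot tell a value taken before the tablet from one taken after it. Because it selects the latest record, it prefers the post-dose value whenever there is one.

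The children exposed to this error are those examined again after their first tablet. Protocol 1.2 and 1.4 expect local allergic reactions in the first few days of treatment, and the examination in Protocol 11.11 covers lips, mucosa, tongue, lungs and skin, where such reactions could be seen. At stake is the accuracy of the shift tables, which for physical examination are the planned tabulation of results.

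**Working it through.** No arithmetic applies, and the plan states no figure on this point. The check traces the rule through the visit schedule and the planned outputs.

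**1. Which records qualify.** Under SAP 6.1 a record qualifies if it is dated on or before the day of first intake. Neither its clock time nor whether the visit was scheduled matters. Among qualifying records the latest is used.

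**2. What would be displaced.** Scheduled times come from the flow chart and outputs from SAP 6.9.3.

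| Assessment | Scheduled up to first intake | Value displaced by an unscheduled post-dose record on dosing day | Planned output |
|---|---|---|---|
| Physical examination | V1, V2 | V2 | Shift table to EOT |
| Safety laboratory tests | V1 | V1 | Shift table to EOT; chemistry and haematology also by visit |
| Vital signs | V1 | V1 | By-visit summary |
| Lung function | V2 | V2 | By-visit summary |

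**3. How a post-dose record can arise.** There are two routes.
- An unscheduled assessment is made on dosing day after intake. The flow chart permits this for all four rows.
- A visit 2 assessment is done after intake, which the preferred order does not rule out. This route exists only for assessments scheduled at V2. For physical examination, the late V2 record would then replace the pre-dose V1 record.

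No measurement is scheduled after the dose on that day, so without one of these routes the rule gives a correct pre-dose baseline.

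**4. Effect on a shift table.** Take a child who is normal before dosing and has an abnormal post-dose record the same day (an assumed pattern).

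| Visit 6 | Baseline as SAP 6.1 is worded | Baseline restricted to before intake |
|---|---|---|
| Normal | Abnormal to normal | Normal to normal |
| Abnormal | Abnormal to abnormal | Normal to abnormal |

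The first row is a false improvement. The second masks a worsening at end of treatment.

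**5. Outputs that do not depend on the rule.** TEAE status uses the time of first dose. SAP 6.9.2.2 also tabulates day 1 onset in minutes for the most frequent IMP-related TEAEs, summarises the six ESI types and lists individual ESIs. Protocol 11.11 sends significant post-screening examination findings that meet the AE definition to an AE page. The primary model in SAP 6.3.2 contains treatment, cohort, age group and pollen station, with no baseline value, and the key secondary endpoints use the same model. The immunology analyses in SAP 6.7.2 do use baseline, but their scheduled baseline sample is at V1. They would change only if an unscheduled post-dose sample were drawn on dosing day.

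**The case against.** The best defence is that the trigger is uncommon and its consequences are limited. The scheduled visit 2 assessments are listed before intake. Bracketed unscheduled assessments are at the investigator's discretion. Protocol 9.3 concerns anaphylaxis and does not say that the arranged visit falls on the same day, and no section requires an unscheduled visit for the expected transient local reactions. All of this stands. It limits how often the rule goes wrong but does not change what the rule selects when a post-dose record exists.

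A reader might infer that the rule hides first-dose reactions. The documents do not support that. Reactions reach the report through TEAE and ESI outputs that make no use of baseline. A baseline-to-EOT shift table would not show a resolved day 1 reaction under a pre-dose baseline either, as the first row of the last table shows.

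A reader might also infer that lung function or blood pressure would be reported as improving on treatment. SAP 6.9.3 plans by-visit summaries for these and specifies no change from baseline, so only a baseline row, if one is shown, could be wrong.

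Finally, a reader might call the date rule and the time rule a contradiction. One selects measurement values and the other classifies events. Using different cut-offs for them is imprecise, and it lets the same post-dose finding count as both treatment-emergent and baseline, but the two rules can be applied together.

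**Conclusion.** The point holds and is minor. As worded, SAP 6.1 can take a post-dose value as baseline, giving either a false abnormal-to-normal shift or a masked normal-to-abnormal shift in the physical examination and laboratory tables. Baseline rows for vital signs or lung function are open to the same error. The primary and key secondary efficacy results and the reporting of reactions as adverse events are unaffected.

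The conclusion assumes that the rule is programmed literally and that at least one child has a post-dose record on dosing day. The number of such children is probably small, because it takes an unscheduled or out-of-order assessment, but it cannot be computed: the documents give no rate for either. It is also tempting to say that the error falls mainly in the active arm, because early local reactions are expected with the tablet. That is a reasonable guess, but the documents give no count by arm to support it.

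**What to change.** In SAP 6.1, replace the date cut-off with three conditions:

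- Baseline is the latest non-missing observation before the date and time of first IMP intake.
- Scheduled V1 and V2 assessments without a recorded time count as taken before intake.
- Unscheduled records dated on the day of first intake are used only if they are documented as taken before intake.

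The last condition also covers dosing postponed under Protocol 9.2. A documented pre-dose check on the later day can serve as baseline; an undocumented one falls back to the V1 or V2 value. One gap remains: a V2 assessment done after intake but without a recorded time would still be treated as pre-dose.

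The cost is a short wording change and a matching condition in the derivation program, with no new data. The day 1 table in minutes already presupposes that dose time is available; the documents do not say whether assessment times are recorded, which is why the second and third conditions are needed. If the change is made after the SAP is final, Protocol section 15 already provides for documenting it in the ICTR.
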